5.3.1 INCB024360

INCB024360 is neither a substrate nor an inhibitor or inducer of cytochrome P450 enzymes. Analysis of human plasma samples indicated that INCB024360 is metabolized by 2 major pathways: O-glucuronidation and reduction. The identification of the 2 major pathways and the enzymes responsible for those pathways has enabled the refinement of the inclusion/exclusion criteria around concomitant medications. However for safety purposes, the case report form must capture the concurrent use of all other drugs, over-

the-counter medications, or alternative therapies.

Hypothetically, inhibition of IDO could cause an increase in serotonin levels that could precipitate a cluster of AEs termed serotonin syndrome. This rare syndrome has been associated with some MAO inhibitors and with combinations of serotonergic drugs.

Symptom onset is usually rapid, often occurring within minutes, and encompasses a wide range of clinical findings:

- Mild symptoms may only consist of increased heart rate, shivering, sweating, dilated pupils, myoclonus, and over responsive reflexes.
- Moderate symptoms include additional abnormalities such as hyperactive bowel sounds, high blood pressure, and hyperthermia. A temperature as high as 40°C (104°F) is common in moderate intoxication. Mental status changes include hypervigilance and agitation.
- Severe symptoms include severe increases in heart rate and blood pressure that may lead to shock. In life-threatening cases, temperature may rise to above 41.1°C (106.0°F). Other abnormalities include metabolic acidosis, rhabdomyolysis, seizures, renal failure, and disseminated intravascular coagulation; these effects usually arise as a consequence of hyperthermia.

At this writing, no laboratory test exists for serotonin syndrome; therefore diagnosis is by symptom observation. Management is based primarily on stopping the usage of the precipitating drugs, the administration of serotonin antagonists such as cyproheptadine, and supportive care including the control of agitation, autonomic instability, and hyperthermia. Additionally, those who ingest large doses serotonergic agents may benefit from gastrointestinal decontamination with activated charcoal if it can be administered within an hour of overdose. The intensity of therapy depends on the severity of symptoms. If the symptoms are mild, treatment may only consist of discontinuation of the offending medication or medications, offering supportive measures, giving benzodiazepines for myoclonus, and waiting for the symptoms to resolve. Moderate cases should have all thermal and cardiorespiratory abnormalities corrected and can benefit from serotonin antagonists. As mentioned above, the serotonin antagonist cyproheptadine is the recommended initial therapy. Additional pharmacological treatment for severe case includes administering atypical antipsychotic drugs with serotonin antagonist activity (e.g., olanzapine). Critically ill patients should receive the above therapies as well as sedation and/or neuromuscular paralysis. Patients who have autonomic instability such as low blood pressure require treatment with direct-acting sympathomimetics, such as epinephrine, norepinephrine, or phenylephrine. Conversely, hypertension or tachycardia can be treated with short-acting antihypertensive drugs such as nitroprusside or esmolol; longer-acting drugs such as propranolol should be avoided as they may lead to hypotension and shock.

As mentioned above, weak cross-reactivity of INCB024360 to the human vasopressin 1a receptor, dopamine receptor, and carbonic anhydrase II may lead to changes in blood pressure or blood electrolytes. In 28-day toxicology studies, C_{max} values have exceeded the IC_{50} for the IDO1 enzyme (72 nM) by up to 37-fold and the IC_{50} for the vasopressin 1a receptor by up to 4-fold (13-fold in single-dose studies) in the absence of any toxicity, so the risk of unintended pharmacological activity is expected to be low.

Studies imply that IDO1 may be a negative inhibition pathway to control autoimmune diseases associated with inflammation. Recent studies with the anti-CTLA-4 antibody ipilimumab have shown dysregulation of mucosal immunity and gastrointestinal toxicity, which manifests as diarrhea. For these reasons, subjects with a history of autoimmune disease should be excluded from participation in this study, and study participants should be closely monitored for signs or symptoms of developing autoimmune or inflammatory disease.

Analysis of human plasma samples indicated that INCB024360 is metabolized by 2 major pathways: O-glucuronidation and reduction. The O-glucuronide (M9) was formed by UGT1A9 and the reduced metabolite (M11) appears to be catalyzed by intestinal microflora. Metabolite M11 is also further metabolized to M12, a product formed by oxidative cleavage catalyzed by CYPs. The identification of the 2 major pathways and the enzymes responsible for those pathways has enabled the refinement of the inclusion/exclusion criteria around concomitant medications. It should be noted that all three major metabolites (M9, M11 & M12) are inactive against IDO1 enzyme.

Use of any UGT1A9 inhibitor including: acitretin, amitriptyline, androsterone, cyclosporine, dasatinib, diclofenac, diflunisal, efavirenz, erlotinib, estradiol (17-beta), flutamide, gefitinib, gemfibrozil, glycyrrhetic acid glycyrrhizin, imatinib, imipramine, ketoconazole, linoleic acid, mefenamic acid, mycophenolic acid, niflumic acid, nilotinib, phenobarbital, phenylbutazone, phenytoin, and probenecid propofol, quinidine, ritonavir, Sorafenib, sulfapyrazone, valproic acid, and verapamil should be avoided from screening through follow-up period.

Low-dose Coumadin (1 mg) is acceptable; however, doses that increase INR are not permitted. If an alternative to Coumadin-based anticoagulants cannot be used, the INR should be monitored weekly after initiation of therapy and upon discontinuation of INCB024360, until INR normalization.

5.3.2 MELITAC 12.1

In several studies, the vaccine has been well tolerated. In the most recent study, in which the adjuvant was Montanide ISA-51 VG alone, Mel44 (n=170), 8% of patients reported unexpected grade 3 treatment-related AEs, plus 10% of patients with grade 3 injection-site ulceration and 7% with grade 3 injection-site induration; the injection-site reactions were expected and not dose-limiting. One grade 4 toxicity was reported (hypoglycemia, <1%). Other common toxicities were evident for approximately 24 hours included fatigue, dyspnea, headache, and myalgia. Mild AEs of rigors/chills, anorexia, nausea, sweating, fever, and flushing were commonly experienced [[[name] 2011](#)].

5.4 Duration of Therapy

Patients with surgically incurable stage III or IV melanoma and tissue amenable to serial biopsy will receive the sequential therapy with INCB024360 alone for 3 weeks followed

by continued INCB024360 plus 6 MELITAC 12.1 vaccines administered intradermally or subcutaneously on days 21, 28, 35, 56, 77, and 98 (weeks 3, 4, 5, 8, 11, and 14).

Serial biopsies will be obtained up to 14 days before starting INCB024360, on day 21 (before the first vaccine), and on day 42 (a week after the third vaccine). When feasible a biopsy will be obtained at week 16 (2 weeks after the sixth vaccination). If possible, tumors will be biopsied from patients coming off study, including for progression of disease.

In the absence of treatment delays due to AE(s), treatment may continue for up to 3 additional cycles of INCB024360 (a total of 4 cycles) after consultation with the trial Principal Investigator, CTEP, and the CITN, or until one of the following criteria applies:

- Disease progression by Response Evaluation Criteria In Solid Tumors (RECIST) or Immune-Related Response Criteria (irRC)
- Intercurrent illness that prevents further administration of treatment
- Unacceptable AE(s)
- Patient decides to withdraw from the study
- General or specific changes in the patient's condition rendering the patient unacceptable for further treatment in the judgment of the investigator

If additional cycles of INCB024360 are deemed appropriate for the patient, the INCB024360 will be given without the administration of the MELITAC 12.1 vaccines.

Only the end of treatment biopsy will be obtained if additional cycles of INCB024360 are approved for each patient.

In patients who are approved to receive additional cycles of INCB024360, a reduced volume of blood will be drawn for specific assays. ([Study Calendar, footnote ***](#))

A delay of up to 60 days between treatment cycles will be allowed.

In the event of unexpected serious AEs related to either component of the combination, treatment of the affected participant with INCB024360 and/or MELITAC 12.1 will be discontinued after analysis by the DSMC, Incyte, and CITN.

5.5 Duration of Follow-up

Patients will be followed for 1 year after removal from study or until death, whichever occurs first. Patients removed from study for unacceptable AE(s) will be followed until resolution or stabilization of the AE. Unacceptable toxicity is defined as any of the following:

- 1) grade 3 or 4 adverse event requiring the patient to be removed from study treatment,
- 2) DLT's of grade 1 treatment related ocular toxicity, grade 2 allergic reactions,
- 3) >2 cm ulceration at the vaccination site or a vaccination adverse event requiring antibiotic treatment, debridement or narcotic management,

NOTE: Chronic inflammatory reactions at the vaccine sites are expected to occur in all participants who receive Montanide ISA-51. Induration may persist for days to months, but is not expected to require additional therapy. Sterile abscesses may occur in some participants. These are not a basis for discontinuation of the vaccines. However, if the inflammatory reactions develop significant ulceration of the skin (> 2 cm), then the patient would be taken off the study, however, this would not be considered a dose-limiting toxicity.

4) any unexpected grade 3 or greater non-hematologic or hematologic toxicity.

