This vaccine was well tolerated. In the most recent Mel44 trial (n=170), 8% of patients reported unexpected grade 3 treatment-related AEs, plus 10% with grade 3 injection-site ulceration and 7% with grade 3 injection-site induration; the injection-site reactions were expected and not dose-limiting. One grade 4 toxicity was reported (hypoglycemia, <1%). Other common toxicities were evident for approximately 24 hours and commonly included fatigue, dyspnea, headache, and myalgia. Mild AEs of rigors/chills, anorexia, nausea, sweating, fever, and flushing were commonly experienced [[[name] 2011](#)]. No concurrent comparator for efficacy was established in the nonrandomized trial of MELITAC 12.1. However, the disease-free survival (DFS) data with this multipeptide vaccine compared favorably to adjuvant trials of high-dose IFN (E1694 clinical trial), favorably with respect to studies E1684 and E1690, and analogously to the Canvaxin trial in patients with resected stage III melanoma. The median DFS was 35 months (2.9 years) with a corresponding 1-year DFS of 76% (95% confidence interval [CI], 60–86%), 2-year DFS of 59% (95% CI, 42–72%), and 3-year DFS of 47% (95% CI, 27–64%). In the more recent Mel43 and Mel44 trials, 3-year DFS was 52% in both trials (95% CI, 43–61%) and overall survival at 3 years was 76% (95% CI, 67–83%) and 79% (95% CI, 71–86%) respectively [[[name] 2009](#); [[name] 2011](#)].

This and similar multipeptide vaccine preparations have been evaluated in prospective randomized Phase II trials with several local adjuvants (e.g., GM-CSF, dendritic cells, incomplete Freund's adjuvant [IFA]), systemic low-dose IL-2, and systemic cyclophosphamide [[[name] 2004](#); [[name] 2007](#); [[name] 2009](#); [[name] 2011](#)]. Vaccination in IFA was more immunogenic than pulsing peptides on dendritic cells, a finding supported by a separate randomized trial [[[name] 2003](#); [O'Neill 2009](#)]. No immunologic or clinical benefit was evident by adding low-dose IL-2, GM-CSF, or cyclophosphamide [[[name] 2004](#); [[name] 2009](#); [[name] 2011](#)]. Thus, the formulation proposed for this trial is peptide in IFA.

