5.1.4 Other Modalities or Procedures: N/A

5.1.5 Investigational Imaging Agent Administration: N/A

5.2 **Definition of Dose-Limiting Toxicity:**

Dose-limiting toxicities (DLTs) include all Grade 3 AEs regardless of investigator attribution or relatedness except for those listed below.

Based on investigator determination the following Grade 3 toxicities can be deemed non-DLT:

- adverse event with a clear alternative explanation (e.g. due to disease progression)
- transient toxicities (≤ 72 hours)
- injection site reactions that are expected and do not require any surgical intervention or repair
- abnormal laboratory values without associated clinically significant signs or symptoms

There are two exceptions to the above. Grade 1 or greater ocular toxicities will be considered a DLT. Grade 2 LFT elevations will be considered a DLT.

In the event of a DLT, it will be determined by the safety team whether both the INCB024360 AND the MELITAC 12.1 will be permanently discontinued. In cases of vaccine injection site reaction or other vaccine related adverse events the INCB024360 may be continued if the vaccine related adverse event continues to show improvement. Management and dose modifications associated with the above adverse events are further outlined in [Section 6](#).

5.3 **General Concomitant Medication and Supportive Care Guidelines**

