5.6 Criteria for Removal from Study

Patients will be removed from study when any of the criteria listed in [Section 5.4](#) applies. The reason for study removal and the date the patient was removed must be documented in the case report form. The patient should be followed per protocol requirements.

AEs will be described and coded based upon the National Cancer Institute Common Terminology Criteria for Adverse Events v4.0 (NCI CTCAE v4.0). Safety will be evaluated by assessing and chronicling treatment-related AEs.

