Thrombocytopenia	Management/Next Dose for INCB024360	Management/Next Dose for MELITAC 12.1
≤ Grade 1	No change in dose	No change in dose
Grade 2	No change in dose	No change in dose
Grade 3	Off protocol therapy	Off protocol therapy
Grade 4	Off protocol therapy	Off protocol therapy
Recommended management: platelet transfusions if indicated		

Fatigue	Management/Next Dose for INCB024360	Management/Next Dose for MELITAC 12.1
≤ Grade 1	No change in dose	No change in dose
Grade 2	No change in dose	No change in dose
Grade 3 or Grade 4	Off Protocol Therapy	Off Protocol Therapy
Recommended management: physician discretion		

Ocular Toxicity	Management/Next Dose for INCB024360	Management/Next Dose for MELITAC 12.1
≤ Grade 1	Off protocol therapy*	Off protocol therapy
Grade 2	Off protocol therapy	Off protocol therapy
Grade 3	Off protocol therapy	Off protocol therapy
Grade 4	Off protocol therapy	Off protocol therapy
*Defined as treatment-related grade 1 ocular toxicities		

Chills/fever/malaise following immunization	Management/Next Dose for INCB024360	Management/Next Dose for MELITAC 12.1
≤ Grade 1	No change in dose	No change in dose
Grade 2	No change in dose	No change in dose
Grade 3	Off protocol therapy if fails to resolve by the next scheduled immunization	Off protocol therapy if fails to resolve by the next scheduled immunization
Grade 4	Off protocol therapy	Off protocol therapy

Injection site reaction	Management/Next Dose for INCB024360	Management/Next Dose for MELITAC 12.1
≤ Grade 1	No change in dose	No change in dose
Grade 2	No change in dose	No change in dose
Grade 3	No change in dose*	No change in dose**
Grade 4	Off protocol therapy	Off protocol therapy

*See section 5.2

** MELITAC 12.1 vaccine may be given if the grade 3 injection site reaction combined area of skin ulceration is <2 cm

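### For a Grade 3 vaccine-site ulcer over 2 cm, Section 5.5 takes the patient off the study while Sections 5.2 and 6 let INCB024360 continue; the ulcer measure and, more narrowly, DLT status also differ

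*Combined protocol and SAP*

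**What the plan says.** **Section 5.5** includes in its definition of unacceptable toxicity ">2 cm ulceration at the vaccination site or a vaccination adverse event requiring antibiotic treatment, debridement or narcotic management". Its note adds that "if the inflammatory reactions develop significant ulceration of the skin (> 2 cm), then the patient would be taken off the study", but that "this would not be considered a dose-limiting toxicity". Section 5.4 lists unacceptable adverse events among the reasons to end treatment. Section 5.6 makes those reasons grounds for leaving the study: "Patients will be removed from study when any of the criteria listed in" Section 5.4 applies.

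**Section 6, injection-site table.** Grades 1 and 2 require no dose change for either agent. Grade 3 requires no dose change for INCB024360, with an asterisk pointing to Section 5.2. For the vaccine, the Grade 3 footnote reads "MELITAC 12.1 vaccine may be given if the grade 3 injection site reaction combined area of skin ulceration is <2 cm". Grade 4 takes the patient off both agents.

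**Section 5.2** allows INCB024360 to go on after an injection-site reaction or other vaccine-related event for as long as the event is improving. It sets no ulcer size. Among the Grade 3 events that an investigator may deem non-DLT it lists "injection site reactions that are expected and do not require any surgical intervention or repair". The Section 6 text first exempts expected Grade 3 injection-site reactions, citing 5.5, and then repeats the conditional list of 5.2.

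**The concern.** The reaction is foreseeable. Section 2.3.2 reports "10% with grade 3 injection-site ulceration" in the most recent vaccine trial, and each vaccination here uses two sites. Yet the consequence of a large ulcer depends on which section a site opens. One ends study participation; the other keeps INCB024360 going and makes only the vaccine conditional.

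Three things are at stake:

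- **Treatment and participation.** Sites could handle the same patient in opposite ways, each in line with the protocol.
- **DLT counts.** These feed the rule in Section 5.1 that stops the study at two DLTs in the first six patients at 300 mg, and the 33% accrual-closure rule in Section 6.
- **Objective 2.** Vaccines on days 21, 28 and 35 precede the day-42 biopsy, which is compared with day 21. A patient taken off the study for a local reaction to those vaccines may not give that sample, and the reason would be tied to the vaccine's inflammatory effect.

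**Working it through.** No numerical figure in the plan rests on this point, so the main check is a comparison of the texts.

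**1. One event, two instructions.** Take a Grade 3 site reaction with a 2.5 cm ulcer.

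| | Section 5.5 (with 5.4, 5.6) | Section 6 table and 5.2 |
|---|---|---|
| Vaccine | stops, patient off study | permission to give it does not apply |
| INCB024360 | stops, patient off study | no dose change; may go on while improving |
| Participation | ends | not ended |
| DLT | no, without condition | non-DLT only if deemed so by the investigator, expected, and without surgery or repair |

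The two agree on withholding the vaccine. They disagree on INCB024360 and on participation. Reading off the study as off treatment does not help, because INCB024360 would still be stopped in one place and continued in the other.

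**2. The measure.** Section 5.5 uses ulceration above 2 cm at the vaccination site. The table uses a combined area below 2 cm, which gives an area in a unit of length.

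- Two ulcers of 1.5 cm, one per site: neither exceeds 2 cm. Summed as lengths they give 1.5 + 1.5 = 3.0 cm, so the table's permission to vaccinate does not apply.
- One ulcer of exactly 2 cm: not above 2 cm, so no removal under 5.5; not below 2 cm, so no permission under the table.
- If the table meant 2 cm², a circular ulcer would reach it at a diameter of 2 × √(2/π) = 1.6 cm, a different boundary again.

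**3. Lower grades.** Section 5.5 also counts as unacceptable toxicity "a vaccination adverse event requiring antibiotic treatment, debridement or narcotic management", whatever the grade. A Grade 2 reaction treated with antibiotics meets that definition, while the table continues both agents.

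**4. How many patients.** Inputs: n = 12 (Section 13.3) and p = 10% Grade 3 ulceration in the earlier trial of 170 patients (Sections 2.3.2 and 5.3.2). Let s be the assumed share of such ulcers that exceed 2 cm and arise before day 42. Expected number = 12 × 0.10 × s; chance of at least one = 1 − (1 − 0.10s)^12.

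| s (assumed) | Expected of 12 | Chance of at least one |
|---|---|---|
| 1.00 | 1.2 | 1 − 0.900^12 = 72% |
| 0.75 | 0.9 | 1 − 0.925^12 = 61% |
| 0.50 | 0.6 | 1 − 0.950^12 = 46% |
| 0.25 | 0.3 | 1 − 0.975^12 = 26% |

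**5. DLT counts.** In the extreme case where every such ulcer counts as a DLT, the chance that ulcers alone give two or more in six is 1 − (1 − p)^6 − 6p(1 − p)^5. At p = 0.10 this is 1 − 0.531 − 0.354 = 11.4%; at p = 0.05 it is 1 − 0.735 − 0.232 = 3.3%. Under the 5.5 wording it is 0.

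**6. Cost of a lost pair.** Without replacement, one loss is 1/12 = 8% of the pairs. The plan states no test, alpha or SD of change. Assuming a two-sided 5% paired t-test, a rise of 1 SD and a within-patient correlation of 0.5, power is 88% with 12 pairs, 85% with 11 and 80% with 10. At correlation 0 it is 61%, 56% and 51%; at 0.75 it is 99%, 99% and 98%.

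**The case against.** Several points on the other side stand.

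- **The table is not an unconditional order.** Its Grade 3 entry for INCB024360 refers to 5.2, where continuation is permissive and depends on improvement. The conflict remains: what 5.2 permits, 5.5 rules out.
- **The DLT conflict is narrow.** For an expected ulcer without surgery or repair that the investigator deems non-DLT, all sections agree. They part when one of those conditions fails, for example an ulcer needing debridement, if that counts as surgical intervention.
- **The sampling loss is softened.** Objective 1 is untouched, since no vaccine precedes day 21. Section 2.4.4 and the calendar call the day-42 biopsy optional, although Table 5.1 does not. Section 13.3 replaces patients without adequate sampling for immune responses, which may or may not cover biopsies. Section 5.5 keeps one year of follow-up, and the calendar has off-study biopsy, FNA and imaging. If vaccine 3 is withheld, a day-42 sample is in any case not one taken a week after the third vaccine.

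A reader might go further and use the 13 of 51 Grade 3 reactions in Table 7.1.4.1: 12 × 13/51 = 3.1 patients and a 97% chance of at least one. The documents do not support that. The figure covers any Grade 3 site reaction, not ulceration, and Section 5.1.3 indicates that those participants received GM-CSF, which this formulation omits. Nor is 72% an estimate, since it treats every Grade 3 ulcer as large enough and early enough. Nor does an ulcer of exactly 2 cm escape both rules; each classifies it, with different consequences.

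**Conclusion.** The contradiction is in the current text and should be corrected. It is firm for INCB024360 and study participation after a Grade 3 ulcer above 2 cm, and for lower-grade reactions that need antibiotics, debridement or narcotics. The measures are not interchangeable. DLT status conflicts only in the narrower case.

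The effect on day-42 sampling is possible but not measurable from the documents. The ceiling of 1.2 of 12 patients assumes that the earlier 10% rate carries over to this combination and that ulcers above 2 cm are among those graded 3; the shares below the ceiling are assumptions. A reader might infer that the plan will lose Objective 2 data, or that 5.5 is the section in error. The documents establish neither. They show only that the passages cannot all be followed.

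**What to change.** The sponsor should reconcile Sections 5.2 and 5.5 and the Section 6 text and table into one rule for vaccine-site reactions, cross-referenced from each place. The rule should:

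- state separately the consequence for the vaccine, for INCB024360 and for study participation, including whether already scheduled sampling continues;
- use one ulcer measure (per site or combined), one unit and one boundary that assigns exactly 2 cm;
- give one DLT status, covering ulcers that need debridement or other surgical treatment;
- say how a reaction needing antibiotics, debridement or narcotics relates to the grade rows of the table.

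Which clinical rule applies is for the sponsor to decide. The cost is a wording amendment and its notification to the 3 or 4 sites; sample size and visit schedule need not change.
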